14.5. Primary Analysis

Vision Satisfaction in Bright Lighting

Subjects' responses will first be categorized into a binary outcome of 1 if the response is positive (Agree or Strongly Agree) or 0 otherwise (Neither Agree Nor Disagree, Disagree or Strongly Disagree). The outcome will then be analyzed using a generalized linear mixed model for correlated binary data. The model will include treatment group (Test, Control), evaluation period (2-week, 4-month and 12-month) and group by evaluation period as fixed factors, and site as random effect (G-side). The model will be adjusted for baseline values, country, age, gender and race as fixed covariates when appropriate. The correlation between responses from the same subjects across evaluation periods will be modeled using an unstructured (UN) covariance matrix (R-side). If problem of convergence encountered, a Compound Symmetry (CS) covariance structure will be considered.

The null and alternative hypotheses for the primary hypothesis are as follows:

$$\begin{aligned} H_0: OR &\leq 1 \\ H_A: OR &> 1; \end{aligned}$$

where OR is the overall odds ratio of having a positive rating of vision satisfaction in bright lighting (Test over Control). The superiority test will be based on the OR and corresponding 95% confidence interval calculated using the final selected model. The lower bound of the 95% confidence interval will be compared to 1. If the lower bound is above 1, the Test lens will be considered superior to the Control lenses with respect to vision satisfaction in bright lighting. The odds ratio at 2-week, 4-month and 12-month evaluation periods will be calculated with their corresponding adjusted 95% confidence intervals to test the secondary hypothesis #1.

This is an observational study and the treatment assignment is not randomized. The Test and Control groups may have large differences on their baseline characteristics, and these differences can lead to biased estimates of treatment effects. Instead of adjusting the model to all covariates including interactions with treatment group and higher order terms, the propensity score will be used. The propensity score, defined as the conditional probability of

being in Test or Control group given the covariates, will be used to balance the covariates in the two groups, and therefore reduce this bias. The propensity will be calculated using a logistic regression model.

A generalized linear mixed model for correlated ordinal data may be considered if the proportion of subjects with positive response is low. Cumulative odds ratio will be used for hypothesis tests.

14.6. Secondary Analysis

Overall Quality of Vision and Overall Comfort

Overall quality of vision and overall comfort ratings will be analyzed separately using the same statistical method described in the primary analysis. The hypothesis tests will be conducted using adjusted 95% confidence intervals of odds ratios.

Pulfrich Effect

The proportion of subjects who experienced the Pulfrich effect will be calculated as the proportion of subjects who disagree or strongly disagree with the statement “While wearing these lenses, my depth perception of moving objects has NOT been impacted”. The Pulfrich effect will be evaluated over time at 2-week, 4-month and 12-month evaluation periods. The proportion of subjects who experienced the Pulfrich effect at least once will also be calculated.

Serious and Significant Ocular AEs

No statistical hypothesis will be tested. The following will be calculated:

1. Incidence rate of serious and significant ocular AEs (in patient-year) will be calculated as follow:

$$IR = \frac{\text{Number of subjects with an event}}{(\text{Sum of subjects' exposure times})/365.25}$$

Where each subject's exposure time is defined as number of days in the study after the enrollment, censored only by events such as first serious or significant ocular AE, dropouts, death or the end of the study.

2. Proportion of subjects with at least one reported serious or significant ocular AE at each evaluation period.
3. Proportion of eyes with at least one reported serious or significant ocular AE at each evaluation period.
4. Proportion of all reported serious and significant ocular AEs at each evaluation period.

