2.2. Endpoints

All of the primary and secondary endpoints will be assessed using the follow-up questionnaire administered at 2-weeks, 4-months and 12-months after the enrollment visit (Visit 1).

Primary endpoints

Vision Satisfaction in Bright Lighting

Subjects will be asked to evaluate their vision satisfaction in bright lighting by rating their level of agreement with the statement “I was satisfied with the quality of my vision in bright lighting with these contact lenses” using a 5-point agreement Likert scale (1: Strongly Disagree, 2: Disagree, 3: Neither Agree nor Disagree, 4: Agree and 5: Strongly Agree).

Secondary endpoints

Overall quality of vision

This will be assessed subjectively using the item “I am satisfied with the overall quality of my vision with these contact lenses”. The item uses a 5-point agreement scale (1: Strongly Disagree to 5: Strongly Agree)

Pulfrich Effect

This will be assessed subjectively using the item “While wearing these lenses, my depth perception of moving objects has NOT been impacted”. Subjects who disagree or strongly disagree with the statement will be considered to have experienced the Pulfrich effect.

Overall comfort

This will be assessed using the item “How would you rate the overall comfort of these contact lenses?”. The item uses the 5-point satisfaction scale, 1: Excellent, 2: Very Good, 3: Good, 4: Fair and 5: Poor.

Reported serious and significant ocular adverse events:

Incidence rate serious and significant ocular adverse events during the study period will be calculated (in 100 patient-year) using all available data from the entire study.

Other endpoint(s):

1. Overall satisfaction
2. Cosmetic appearance assessment
3. Lens storage compliance
4. Reasons for discontinuations
5. All reported ocular and non-ocular adverse events
6. Other subjective assessments (indoor performance, overall opinion, average wear time, etc.)

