14. STATISTICAL METHODS

14.1. General Considerations

Statistical Analysis will be undertaken by the sponsor or under the authority of the sponsor. A general description of the statistical methods to be implemented in this clinical trial is outlined below. More details will be included in the stand-alone Statistical Analysis Plan (SAP). The SAP will be finalized prior to database lock.

All data summaries and statistical analyses will be performed using the SAS software 9.4 or higher (SAS Institute, Cary, NC).⁷ Throughout the analysis of data, the results for each subject/eye will be used when available for summarization and statistical analysis.

Summary tables (descriptive statistics and/or frequency tables) will be provided by arm for all baseline variables, ECP registration questionnaire (ERQ), Patient registration questionnaire (PRQ), and 2-week, 4-month and 12-month survey questionnaires. Continuous variables will be summarized with descriptive statistics (n, mean, standard deviation (SD), median, minimum and maximum). Frequency count and percentage of subjects or eyes within each category will be provided for categorical data.

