14.4. Level of Statistical Significance

All planned analysis for this study will be conducted with an overall type I error rate of 5%. The secondary analysis will be adjusted for multiple comparisons between the Test and the Control groups across the evaluation periods using a simulated-based approach (Edward and Berry).¹⁵

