14.8. Interim Analysis

There will be three interim analyses once 50% of enrolled subjects have completed the 2-week, 4-month and 12-month questionnaires. The interim data will be summarized using descriptive statistics. Reasons for dropouts and ocular adverse events will be monitored. An interim statistical analysis plan (ISAP) may be considered, if necessary, for further analysis prior to the database lock.

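### Does the unstated cut on the comfort scale leave the test of secondary hypothesis 3 open to a late choice?

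*Combined protocol and SAP*

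**What the plan says.** Section 14.5 turns the primary item into a "binary outcome of 1 if the response is positive (Agree or Strongly Agree) or 0 otherwise", and lists the three remaining agreement categories as 0. It then fits a generalized linear mixed model and tests an odds ratio. An ordinal model is optional if positive responses are few.

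Section 14.6 extends this: "Overall quality of vision and overall comfort ratings will be analyzed separately using the same statistical method described in the primary analysis". It tests both items with adjusted 95% confidence intervals of odds ratios.

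Section 2.2 gives overall quality of vision the same agreement scale as the primary item. Comfort is different: "The item uses the 5-point satisfaction scale, 1: Excellent, 2: Very Good, 3: Good, 4: Fair and 5: Poor". Section 2.3 makes superior comfort, over one year and at each period, secondary hypothesis 3.

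On timing, section 14.1 calls section 14 a general description, puts further detail in a stand-alone SAP, and adds: "The SAP will be finalized prior to database lock". Section 14.8 says: "There will be three interim analyses once 50% of enrolled subjects have completed the 2-week, 4-month and 12-month questionnaires". Those analyses are descriptive, and the matters named for monitoring are reasons for dropout and ocular adverse events.

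On error control, section 14.4 sets 5% overall and adds: "The secondary analysis will be adjusted for multiple comparisons between the Test and the Control groups across the evaluation periods".

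**The concern.** An odds ratio needs a defined positive response, and the labels that define it in section 14.5 do not exist on the comfort scale. The doubtful category is *Good*. By position it matches the neutral middle of the agreement scale, which scores 0. By wording it is favourable, which suggests 1. Overall quality of vision has no such difficulty.

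Timing makes this look worse. The SAP may be finalized as late as database lock, and three interim summaries come before that. Section 14.1 says of the general tables that "Summary tables (descriptive statistics and/or frequency tables) will be provided by arm for all baseline variables", and the same sentence goes on to the survey questionnaires. The study is open label. Someone could therefore see comfort frequencies by arm and then settle the cut. The multiplicity rule in section 14.4 covers evaluation periods, not a choice between cuts. The 5% claim for hypothesis 3 would be at stake.

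**Working it through.** **1. The two scales side by side** (sections 2.2 and 14.5)

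| Rank, best first | Agreement item (code) | Score in 14.5 | Comfort item (code) | Score carried over by rank |
|---|---|---|---|---|
| 1 | Strongly Agree (5) | 1 | Excellent (1) | 1 |
| 2 | Agree (4) | 1 | Very Good (2) | 1 |
| 3 | Neither (3) | 0 | Good (3) | 0 |
| 4 | Disagree (2) | 0 | Fair (4) | 0 |
| 5 | Strongly Disagree (1) | 0 | Poor (5) | 0 |

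Carrying the rule over by numeric code (4 and 5 positive) would score Fair and Poor as successes. That contradicts a hypothesis of superior comfort, so nobody would do it. Carrying it over by rank gives the best two of five. Counting *Good* as well makes it the best three of five, which is a different dichotomization from the one section 14.6 refers to.

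**2. What a data-driven choice would require**

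Interim tables would have to (a) be split by arm, (b) include comfort, (c) come before the cut is set, and (d) influence it. Section 14.8 states none of these. The by-arm sentence in section 14.1 describes summary tables in general and does not mention the interims. The lock date is a deadline for the SAP; it does not show when the cut was or will be set.

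**3. How large the effect would be if all four held**

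The plan gives no comfort rates and no comfort sample size, so there is no figure of its own to reproduce. Simulated ratings were used instead: six assumed control distributions (best two categories 30-80%, best three 65-94%) and three levels of within-subject correlation. With no true difference, the correlation *r* between the test statistics of the two cuts was 0.60-0.68.

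The chance that at least one cut exceeds a threshold *c* is 1 − Φ₂(c, c; r), where Φ₂ is the bivariate normal distribution function.

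- *c* = 1.96 (unadjusted): 4.4% at r = 0.60 and 4.2% at r = 0.68, against 2.5% for one fixed cut. If the cut is picked on the first half of subjects and tested on all, simulation gives 3.8-3.9%.
- A separate simulation, treating ratings as an effective number of independent ones, gives 4.5-4.8% for picking at the end.
- Section 14.6 calls for adjusted intervals. For three periods with a common correlation of 0.7 to 0.2, the simulated critical value is 2.30 to 2.38.
- *c* = 2.30: 1.9% at either r. *c* = 2.38: 1.6% at r = 0.60 and 1.5% at r = 0.68. So if the adjusted interval also covers the one-year odds ratio, that test stays below 2.5% even after picking the better cut.
- If success at any single period counts, the family rate is about 4.3-4.5%, against 2.5% for one cut.

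**4. Power under each cut**

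Take 240 per arm, 3 ratings, within-subject correlation 0.5 and a common odds ratio of 1.5. The effective number per arm is 240 × 3 / (1 + 2 × 0.5) = 360. Unadjusted two-sided 5% test, assumed control rates:

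| Best two, control | Power | Best three, control | Power |
|---|---|---|---|
| 40% | 77% | 75% | 60% |
| 50% | 77% | 85% | 44% |
| 60% | 74% | 90% | 32% |

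For the middle row, best two: the odds go from 1.0 to 1.5, so 50% becomes 60%. Then (0.10 − 1.96 × √(2 × 0.55 × 0.45 / 360)) / √((0.25 + 0.24) / 360) = 0.74, which is a power of 77%. In these scenarios the rank carry-over is also the more powerful cut, so the sponsor would have no general reason to prefer the other.

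**5. Disagreement between the cuts**

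With a true cumulative odds ratio of 1.3 to 1.5, 240 per arm and one assumed latent correlation (0.70), the two cuts reach different conclusions in about 22-39% of simulated trials. This shows that they have different power. It is not an error rate, since either cut is valid if fixed beforehand.

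**The case for a change.** The best case for a change is that the remedy is cheap and the omission stands out. Section 14.5 lists all five categories of its item, and section 14.6 names the categories that define the Pulfrich effect. Comfort is the only hypothesis-tested item without a mapping. Section 14.10 has changes from the planned analysis documented, but with no comfort cut in section 14, a late choice might not be recognized as a change. Descriptive by-arm tables would be enough to show which cut looks better. The ordinal option does not help, because its trigger depends on the positive proportion, and so on the cut.

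Part of this stands. The mapping is not written in the available text, and nothing there guarantees that it is fixed before comfort data are seen. Inflation is possible where any single period counts as success.

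The argument from section 14.10 is weaker than it looks. If the best two categories are what the same method implies, adding *Good* departs from that method and would need documenting and justifying. The ordinal trigger is undefined for the primary endpoint too, so it is a separate matter. That a sentence is cheap does not make the plan unsound without it.

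**Conclusion.** No change to the plan follows. This is a missing detail that an analyst following section 14.6 would fill sensibly, by scoring Excellent and Very Good as positive. Recording that in the stand-alone SAP would write down the rule the plan already implies. The available text cannot show that the SAP lacks it: that SAP is not part of it, and the Appendix A forms are not reproduced.

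The reach is limited to secondary hypothesis 3 in a non-randomized, open-label registry. The possible inflation, from 2.5% to 4.2-4.4% one-sided (4.5-4.8% in the simpler simulation), is a worst case. It assumes invented comfort distributions, an unadjusted threshold, and a choice of cut made after seeing the final data. Under the adjusted intervals it depends on how they are applied: 1.5-1.9% for the one-year test if they cover it, or about 4.3-4.5% if any period can count. The conclusion rests on reading the same statistical method as including the best-two-of-five rule. It would be weaker if the SAP adopted a different cut after comfort results by arm had been seen.

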14.7. Other Exploratory Analyses

Subgroup analysis of the primary and secondary endpoints will be conducted by country, age group and lens material. Other subgroup analysis may be considered by factors showing interaction effects with the treatment. The control group will be categorized by lens materials and/or wear modality for further comparisons with the Test lens.

Further analysis using a generalized linear mixed model using Poisson or negative binomial distribution will be considered to test for statistical difference in incidence rates between Test and Control groups. Non-ocular lens related AEs will be evaluated.

14.8. Interim Analysis

There will be three interim analyses once 50% of enrolled subjects have completed the 2-week, 4-month and 12-month questionnaires. The interim data will be summarized using descriptive statistics. Reasons for dropouts and ocular adverse events will be monitored. An interim statistical analysis plan (ISAP) may be considered, if necessary, for further analysis prior to the database lock.

14.9. Procedure for Handling Missing Data and Drop-Outs

Missing or spurious values will not be imputed. The count of missing values will be included in the summary tables and listings.

Subject dropout is expected to be one of the main reasons of missing data in this registry study. Past clinical trials do not provide the evidence that subject dropout is systematic or not-at-random. To evaluate the impact of missing data, sensitivity analysis will be conducted using multiple imputation. The SAS/STAT procedures PROC MI and PROC MIANALYZE will be utilized with a parametric regression method used to make at least 50 imputations.

14.10. Procedure for Reporting Deviations from Statistical Plan

The analysis will be conducted according to that specified in above sections. There are no known reasons for which it is planned to deviate from these analysis methods. If for any reason a change is made, the change will be documented in the study report along with a justification for the change.

15. DATA HANDLING AND RECORD KEEPING/ARCHIVING

15.1. Case Report Form/Data Collection

The data collected by the investigators for this study will be captured on paper case report forms (CRFs). These will be returned to the CRO and then entered into an electronic data collection (EDC) system.

Once completed, the eCRFs will be reviewed for accuracy and completeness. The sponsor or sponsor's representatives will be authorized to gain access to the subject recordation for the purposes of monitoring and auditing the study.

The questionnaire data will be entered by the subjects into an EDC system. Edit checks, electronic queries, and audit trails are built into the system to ensure accurate and complete data collection. Electronic data will be transmitted to a secure central database as forms are completed or updated, ensuring information accuracy, security, and confidentiality.

The content and structure of the eCRFs are compliant with ISO14155:2011.¹

15.2. Subject Record

At a minimum, the subject record should be available for the following:

- subject identification
- eligibility
- study identification
- provision of and date of informed consent
- a record of all adverse events
- follow-up of adverse events

The subject record is the eCRF or an external record. The author of an entry in the subject record must be identifiable. The first point of entry is considered to be the source record.

16. DATA MANAGEMENT

16.1. Access to Source Data/Document

The Investigator/Institution will permit trial-related monitoring, audits, IEC/IRB review and regulatory inspection(s) by providing direct access to source data/documents. Should the clinical site be contacted for an audit by an IEC/IRB or regulatory authority, JJVC must be contacted and notified in writing within 24 hours.

16.2. Confidentiality of Information

Information concerning the investigational product and patent application processes, scientific data or other pertinent information is confidential and remains the property of JJVC. The Investigator may use this information for the purposes of the study only. It is understood by the Investigator that JJVC will use information developed in this clinical study in connection with the development of the investigational product and therefore may disclose it as required to other clinical investigators and to regulatory agencies. In order to allow the use of the information derived from this clinical study, the Investigator understands that he/she has an obligation to provide complete test results and all data developed during this study to the Sponsor.

16.3. Data Quality Assurance

Steps will be taken to ensure the accuracy and reliability of data, include the selection of qualified investigators and appropriate clinical sites and review of protocol procedures with the Principal Investigator. The Principal Investigator, in turn, must ensure that all Sub-Investigators and clinical site personnel are familiar with the protocol and all study-specific procedures and have appropriate knowledge of the study article.

Training on case report form completion will be provided to clinical site personnel before the start of the study. The Sponsor will review case report forms for accuracy and completeness remotely during the conduct of the study, during monitoring visits, and after transmission to data management. Any data discrepancies will be resolved with the Investigator or designee, as appropriate.

Quality Assurance representatives from JJVC may visit clinical sites to review data produced during the study and to assess compliance with applicable regulations pertaining to the conduct of clinical trials. The clinical sites will provide direct access to study-related source data/documents and reports for the purpose of monitoring and auditing by JJVC and for inspection by local and regulatory authorities.

17. MONITORING

The study monitors will maintain close contact with the Principal Investigator and the Investigator's designated clinical site personnel. The monitor's responsibilities will include:

- Ensuring that the investigation is being conducted according to the protocol, any subsequent amendments, and regulatory requirements are maintained
- Ensuring the rights and wellbeing of subjects are protected
- Ensuring that protocol deviations are documented with corrective action plans, as applicable
- Clarifying questions regarding the study
- Resolving study issues or problems that may arise
- Reviewing of informed consent forms and source documentation verification in accordance with the monitoring plan.

18. ETHICAL AND REGULATORY ASPECTS

18.1. Study-Specific Design Considerations

Potential subjects will be fully informed of the requirements of the study. Subjects will be told that their consent to participate in the study is voluntary and may be withdrawn at any time with no reason given and without penalty or loss of benefits to which they would otherwise be entitled. Only subjects who have provided their consent voluntarily will be enrolled.

